**12.4. Appendix 4: Study Phases**

**12.4.1. Study Phases**

Only Concomitant Medication will be reported by treatment phases and all other displays will be irrespective of the phases.

**12.4.2. Study Phases for Concomitant Medication**

Definition	Treatment Phase	
	Pre-Treatment	On-Treatment*
Subject did not take study treatment (e.g., screening failures) AND concomitant medication stop date >= date of Screening	Y	
Concomitant medication start date < treatment start date AND (date of Screening <= concomitant medication stop date < treatment start date)	Y	
Concomitant medication start date < (treatment start date or screening Date) and the variable that defines the status of Concomitant medication end with respect to reference time -period is ("BEFORE")	Y	
Concomitant medication start date < treatment start date AND the variable that defines the status of Concomitant medication end with respect to reference time -period is ("AFTER", "DURING", "DURING/AFTER", "ONGOING")	Y	Y
Concomitant medication start date < treatment start date AND (treatment start date < concomitant medication stop date <= treatment stop date)	Y	Y
(Concomitant medication start date < treatment start date) AND (concomitant medication stop date > treatment stop date)	Y	Y
Treatment start date <= concomitant medication start date		Y

\*On-Treatment phase includes both On-Treatment and Post-Treatment concomitant medications.

## 12.5. Appendix 5: Data Display Standards & Handling Conventions

### 12.5.1. Reporting Process

Software	

 
The currently supported versions of SAS software (Version 9.2 or higher).
 
	
Reporting Area	
HARP Server	: us1salx00259
HARP Compound	: \ARPROD\GSK2881078\mid200182\
Analysis Datasets	

 
Analysis datasets will be created according to CDISC standards (SDTM IG Version 3.2 & AdAM IG Version 1.0).
 
For creation of AdAM datasets (ADCM/ADAE), the same version of dictionary datasets will be implemented as SDTM.
 
	
Generation of RTF Files	

 
RTF files will be generated for each reporting effort.
 
	

### 12.5.2. Reporting Standards

General	

 
The current GSK Integrated Data Standards Library (IDSL) will be applied for reporting, unless otherwise stated (IDSL Standards Location: https://spope.gsk.com/sites/IDSLLibrary/SitePages/Home.aspx):             
 
4.03 to 4.23: General Principles
 
5.01 to 5.08: Principles Related to Data Listings
 
6.01 to 6.11: Principles Related to Summary Tables
 
7.01 to 7.13: Principles Related to Graphics
 
 
 
	
Formats	

 
GSK IDSL Statistical Principles (5.03 & 6.06.3) for decimal places (DP's) will be adopted for reporting of data based on the raw data collected, unless otherwise stated.
 
Numeric data will be reported at the precision collected on the eCRF except for the parameters specified below.
 
	
Domain	DP for Mean
Leg Press (Last Successful Lift 1-Rep Max (kg))	1 DP
Appendicular Lean Mass (kg) & Total Lean Mass (kg)	3 DP
PRO parameters & SGRQ parameters	2 DP
Total Score for SPPB	1 DP
CAT	1 DP
Time for the Fastest Walk (sec) & Time Repeated Chair Stand Test (sec)	3 DP

Incremental Shuttle Walking test - Maximum Distance Walked (m)	1 DP	
CWR - Exercise Duration (sec)	1 DP	

 
The reported precision from non eCRF sources will follow the IDSL statistical principles but may be adjusted to a clinically interpretable number of DP's.
 
		
Planned and Actual Time		

 
Reporting for tables, figures and formal statistical analyses:                             
 
Planned time relative to dosing will be used in figures, summaries, statistical analyses and calculation of any derived parameters, unless otherwise stated.
 
 
 
Reporting for Data Listings:                             
 
Planned and actual time relative to study drug dosing will be shown in listings (Refer to IDSL Statistical Principle 5.05.1).
 
Unscheduled or unplanned readings will be presented within the subject's listings.
 
 
 
		
Unscheduled Visits		

 
Unscheduled visits will be assigned to a study visit using the assessment windows defined in Section 12.3. After slotting of Un-scheduled visits, if there are multiple assessments at a planned time-point, then the value closest to the target day for that window will be used. If its equidistant from the target day, then mean of the assessments will be used in summary and figures. Listing will show both the planned and un-scheduled assessments.
 
Data summaries will only report visits that are planned assessment time points for each parameter (according to the T&E table) which can include the unscheduled visits if slotted.
 
All unscheduled visits will be included in listings.
 
Unscheduled visits can be included in the derivation of any time post baseline visits and baseline if the definition of baseline is the latest pre-dose visit (See Section 5.2).
 
		
Descriptive Summary Statistics		
Continuous Data	Refer to IDSL Statistical Principle 6.06.1	
Categorical Data	N, n, frequency, %	
Graphical Displays		

 
Refer to IDSL Statistical Principals 7.01 to 7.13.
 
		

## 12.6. Appendix 6: Derived and Transformed Data

### 12.6.1. General

Multiple Measurements at One Analysis Time Point

 
• Mean of the measurements (not in case of visit slotting) will be calculated and used in any derivation of summary statistics but if listed, all data will be presented.
 
• If there are two values within a time window (as per Section 12.3.1) the value closest to the target day for that window will be used. If values are the same distance from the target, then the mean will be taken.
 
• Participants having both High and Low values for Normal Ranges at any post-baseline visit for safety parameters will be counted in both the High and Low categories of “Any visit post-baseline” row of related summary tables. This will also be applicable to relevant Potential Clinical Importance summary tables.
 

Study Day

 
• Calculated as the number of days from First Dose Date: 
 
• Ref Date = Missing → Study Day = Missing
 
• Ref Date < First Dose Date → Study Day = Ref Date – First Dose Date
 
• Ref Date ≥ First Dose Date → Study Day = Ref Date – (First Dose Date) + 1
 
 
 
 
Note that Treatment Start Date is considered as Study Day 1.

Post-baseline

 
• Post-baseline refers to the combined time periods of On-treatment and Post-treatment.
 

Change from Baseline
= Post-baseline - Baseline
Ratio to Baseline
= $\exp(\log(\text{Post-baseline}) - \log(\text{Baseline}))$
Percent Change from Baseline
= $100 * (\text{Post-baseline} - \text{Baseline}) / \text{Baseline}$
Treatment compliance

= <math>100 * (\text{Total Amount Taken} / (\text{Treatment duration in days} * 2))</math>
 
Total Amount Taken = Total tablets dispensed – Total tablets returned – Total tablets lost.

### 12.6.2. Efficacy

Secondary Efficacy endpoints
Peak performance from incremental shuttle walking test

 
• ‘Maximum distance walked’ collected from incremental shuttle walk test in CRF
 

Constant Work Rate (CWR) duration from endurance shuttle walking test

 
• ‘Exercise duration time (seconds)’ collected from endurance shuttle walk test in CRF
 

St George Respiratory Questionnaire (SGRQ) total score and domains

 
• The total score and three component scores (Symptoms, Activity and Impacts) will be derived from St George Respiratory Questionnaire- COPD (SGRQ- c) raw scores based upon the score manual (ST
 

**Secondary Efficacy endpoints**

GEORGE'S RESPIRATORY QUESTIONNAIRE FOR COPD PATIENTS (SGRQ-C) Version No.1.3  
March 2016)

- First, sum the weights for all items with a positive response:  
Symptoms component consists of all the questions (question 1 -7) in Part 1. The weights for Questions 1-7 are summed. A single response is required to each item. If multiple responses are given to an item, the weights for the multiple positive responses should be averaged then added to the sum.  
  
Activity component is calculated from the summed weights for the positive responses to items questions 9 and 12 in Part 2 of the questionnaire.  
  
Impacts component is calculated from questions 8, 10, 11, 13, 14 in Part 2 of the questionnaire. The weights for all positive responses to items in Questions 10, 11, 13 are summed together with the responses to the single item that should have been checked (ticked) in Questions 8 and 14. In the case of multiple responses to either of these items, the average weight for the item should be calculated.  
  
Total score is calculated by summing the weight to all the positive responses in each component.
- Then, calculate the score:  
The score for each component is calculated separately by dividing the summed weights by the maximum possible weight for that component and expressing the results as a percentage:  
Sum of maximum possible weights for each component and Total:  
Symptoms: 566.2    Impact: 1652.8  
Activity:    982.9    Total:    3201.9
- Last, converting SGRQ-c scores to be comparable to SGRQ:  
The adjustment is:  
Symptoms:  $SGRQ \text{ score} = (SGRQ-C \times 0.99) + 0.94 \text{ units}$   
Activity:  $SGRQ \text{ score} = (SGRQ-C \times 0.87) + 7.01 \text{ units}$   
Impacts:  $SGRQ \text{ score} = (SGRQ-C \times 0.88) + 2.18 \text{ units}$   
Total:  $SGRQ \text{ score} = (SGRQ-C \times 0.90) + 3.10 \text{ units}$
- Handling of missing items  
A Total score can be calculated in the presence of missing data, but only if the domains meet their 'missing items' rules (see below). If one domain exceeds its permitted number of missed items, then a total score cannot be calculated.  
Symptoms: The Symptoms component will tolerate a maximum of 1 missed item. The weight for the missed item is subtracted from the total possible weight for the Symptoms component (566.2) and from the Total weight (3201.9) and then calculate the score.  
Activity: The Activity component will tolerate a maximum of 3 missed items. The weight for the missed item (s) is subtracted from the total possible weight for the Activity component (982.9) and from the Total weight (3201.9) and then calculate the score.  
Impacts: The Impacts component will tolerate a maximum of 5 missed items. The weight for the missed item (s) is subtracted from the total possible weight for the Impacts component (1652.8) and from the Total weight (3201.9) and then calculate the score.
- Responder is defined as 'Yes' when the total score at a post-baseline visit decreases by 4 or more from baseline total score, otherwise, non-responder.

Secondary Efficacy endpoints		
Total Short Physical Performance Battery (SPPB) score and times for chair rise and 4 m gait speed		

 
Total SPPB score, 'Time for five stands done successfully' collected for chair and 'time for fastest walk for 4 m gait test' collected from CRF will be used, respectively
 
SPPB at baseline will be categorized as below: SPPB 10-12 points fit patient, normal  SPPB 8-9 points pre-frail patient  SPPB ≤ 7 points frail patient
 
		
COPD Assessment Test (CAT)		

 
Total score of 8 questions will be used
 
Responder is defined as 'Yes' when the total score at a post-baseline visit decreases by 2 or more from baseline total score, otherwise, non-responder.
 
If one or more of the 8 questions are missing the total score and the responder will be missing.
 
		
PROactive endpoints (individual components (Difficulty and Amount) and total score)		

 
The PROactive instrument (IMI PROACTIVE IN COPD DAILY AND CLINICAL INSTRUMENTS D-PPAC and C-PPAC 2016 (Use D-PPAC for the calculation of scores)) combines a PRO questionnaire and an activity monitor to measure physical activity in COPD patients. It is 9-item daily assessments covering 2 different domains (amount and difficulty) designed for electronic administration. The 'amount' domain is covered by 2 items (questions - amount of walking outside and chores outside) and by 2 activity monitor outputs (vector magnitude units per minute (VMU/min) and steps/day). The 'difficulty' domain is covered by 5 items (questions).
 
The scores for activity monitor outputs, step counts and VMU's is assigned based on the 5 level categories they are falling in (see the table below).
 
		
Scores	VMU/min	Steps/day

CCI - This section contained Clinical Outcome Assessment data collection questionnaires or indices, which are protected by third party copyright laws and therefore have been excluded.
		

 
Calculation of daily score for each domain (amount, difficulty) and total score: First, domains are scored by simple adding items, which, the values are 0-17 for 'amount' and 0-20 for 'difficulty'. The raw scores are then scaled to a score ranging from 0 to 100, based on Table 1 in the guidance (see Reference)  The 'total score' is obtained calculating the average between two domains. This score has the same scale of two individual domains, from 0 to 100.  PROactive scores for a day cannot be calculated if the subjects missed any of the 9 items in any day.
 
		

Secondary Efficacy endpoints	

 
Calculation of the weekly score for each domain (amount, difficulty) and total score: The average of the daily scores during a 7-day period will be the weekly score separately for each domain (amount, difficulty) and total score.
 
Score eligibility: Adequate physical activity data are considered for days where more than eight hours of wearing time is available. The activity monitor measurement days used should be concurrent with the questionnaire.
 
 
At least four days with <math>\geq 8</math> hours of wearing time of activity monitor data are required for the measurements to be valid for a weekly average. These four days should be in the same week (7 days from the first day of assessments), do not need to be consecutive, and could cover weekdays or weekend days without distinction.
	

Physical Activity Measures	

 
At least four days with <math>\geq 8</math> hours of wearing time of activity monitor data are required for the measurements to be valid for a weekly average. These four days should be in the same week (7 days from the first day of assessments), do not need to be consecutive, and could cover weekdays or weekend days without distinction. Then calculate the average by dividing total with number of days.
 
The physical activity measures weekly average steps, weekly average vector magnitude unit/wear time and weekly average moderate/vigorous activity duration have the same derivation.
 
The number of subjects included: The count of subject in each visit who has wear time more than 8 hours for at least 4 days in a week.
 
Average number of days included per subject: This the average number of days with wear duration more than 8 hours for at least 4 days in each visit.
 
Average number of minutes included per subject: This the average wear duration in minutes for those subjects with more than 8 hours of wear duration for at least 4 days in a week for each visit.
 
	

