6.1. Inclusion Criteria

Participants are eligible to be included in the study only if all of the following criteria apply:

1. Participant must be 50 to 75 years of age inclusive, at the time of signing the informed consent.
2. Male and/or female:

a. Male participants:

A male participant with a partner who is a woman of child bearing potential (WOCPB) must agree to use contraception as detailed in [Appendix 2](#) of this protocol during the treatment period and for at least 5 half-lives of study medication have passed after the last ingested dose [125 days, corresponding to time needed to eliminate study treatment for both genotoxic and teratogenic study treatments *plus* an additional 90 days (a spermatogenesis cycle) for study treatments with genotoxic potential] after the last dose of study treatment and refrain from donating sperm during this period.

b. Female participants:

A female participant is eligible to participate if she is post-menopausal and not a woman of childbearing potential (WOCBP) as defined in [Appendix 2](#). Note: Postmenopausal is defined as 12 months of spontaneous amenorrhea [in questionable

cases a blood sample with simultaneous follicle stimulating hormone (FSH) levels consistent with menopause (refer to laboratory reference ranges for confirmatory levels), or be >60 years of age].

3. Confirmed diagnosis of COPD in accordance with the ATS/ERS criteria [Celli, 2004] with a post-bronchodilator FEV₁/ forced vital capacity (FVC) < 0.70 AND 30% ≤ FEV₁%predicted ≤65% of predicted normal value calculated at Screen using the Quanjer reference equation [Quanjer, 2012].
4. Short Physical Performance Battery (SPPB) with ALL of the following:
 - Timed chair stand score ≥1 AND ≤3
 - No score of “0” on any component of the SPPB (i.e., gait speed, balance, or timed chair stand)
5. Body Mass Index (BMI) within the range 18 - 32kg/ m² (inclusive), where BMI = (weight in kg) / (height in meters)²
6. Current smokers OR former smokers with a cigarette smoking history of ≥10 pack years (1 pack year =20 cigarettes smoked per day for 1 year or equivalent). Former smokers are defined as those who have stopped smoking for at least 6 months prior to Baseline.
7. Participants must be able to read and write in the language used for the provided electronic diary and be able to operate an electronic device to a level that allows them to complete an electronic diary on a daily basis.

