6.4. Screen Failures

Screen failures are defined as participants who consent to participate in the clinical trial but are never subsequently randomized. A minimal set of screen information is required to ensure transparent reporting of screen failure participants, meet the Consolidated Standards of Reporting Trials (CONSORT) publishing requirements, and respond to queries from Regulatory authorities. Minimal information includes demography, screen failure details, eligibility criteria, and any serious SAEs.

Participants are expected to meet study entry criteria when they are randomized. If a participant initially qualifies for the study and their condition changes prior to randomization such that they no longer qualify for the study, the participant should be considered a screen failure. Participants who experience a moderate/severe exacerbation of COPD in the period after the screening visit AND before the baseline visit should be considered a run-in failure, however these participants may be eligible for rescreening at a later date. Note: Participants who fail screen may be rescreened if, in the opinion of the investigator, the participant's condition was transient and the participant will qualify for the study at a later date during the study enrolment period. Participants may be rescreened a maximum of two times in total. Rescreened participants should be assigned a new participant number.

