9.2.3.3. Short Physical Performance Battery (SPPB)

Participants will be assessed for balance, timed rises from a chair, and gait speed, and scored according to published guidelines [Guralnik, 1994]. The scores for each component and the time in seconds for each component will be recorded. The same study personnel should perform this test wherever possible; site-specific training for this procedure will be given to harmonize data collection procedures prior to participant recruitment.

Short physical performance battery should be undertaken at screening, baseline, day 28, day 56 and day 90 visits.

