10.2. Populations for Analyses

All Participants Population

The 'All Participants Population' is defined as all randomized participants who receive at least one dose of study medication.

Analysis Population

The 'Analysis Population' (AP) is defined as participants in the 'All Participants' population having baseline and at least one post-baseline assessment of the strength, lean mass or functional endpoint.

Per Protocol Population (PP)

The 'Per Protocol Population' will consist of any AP participants who are compliant with protocol-specific criteria and who do not experience an exacerbation during the treatment phase of the study. Participants with specified protocol deviations and those failing to complete the Week 13 functional assessments will be excluded. The Per Protocol population will be used for analysis of strength, lean mass and the functional endpoints.

Pharmacokinetic (PK) Population

The 'PK Population' is defined as participants in the 'All Participants' population for whom a PK sample was obtained and analysed for GSK2881078.

All available data will be used in the analyses as defined in the Populations above. Missing values will not be imputed.

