### 5.2. Baseline Definitions

Parameter	Study Assessments Considered as Baseline			Baseline Used in Data Display
	Screening	Day -9	Day 1 (Pre-Dose)	
Efficacy				
Leg Strength	X		X	whichever is latest*
Incremental Shuttle Walk Test		X	X	whichever is higher
Endurance Shuttle Walk Test			X	Day 1
Dual-energy X-ray Absorptiometry (DXA)			X	Day 1
Short Physical Performance Battery (SPPB)	X		X	whichever is latest*
COPD Assessment Test (CAT)			X	Day 1
Patient Global Rating of Severity (PGRS)			X	Day 1
St George Respiratory			X	Day 1

Parameter	Study Assessments Considered as Baseline			Baseline Used in Data Display
	Screening	Day -9	Day 1 (Pre-Dose)	
Questionnaire COPD (SGRQ-c)				
PROactive Physical Activity	X	X		See detail below**
Spirometry	X		X	whichever is latest*
Sniff Nasal Inspiratory Pressure (SnIP)	X		X	whichever is latest*
Safety				
Vital Signs	X		X	whichever is latest*
12-lead ECG	X		X	whichever is latest*
Haematology	X		X	whichever is latest*
Clinical Chemistry	X		X	whichever is latest*
Urinalysis	X		X	whichever is latest*
hsCRP, Fibrinogen			X	Day 1
Lipid panel	X		X	whichever is latest*
PSA	X		X	whichever is latest*
HbA1c	X			screening
Exploratory				
Cardiac and liver MRI			X	Day 1
Handgrip strength	X		X	whichever is latest*
Reproductive Tissue Biomarkers			X	Day 1
Bone Biomarkers			X	Day 1
***Exploratory Biomarkers			X	Day 1
***Monitored home exercise program		X	X	whichever is latest*

\*Baseline value will be the latest pre-dose assessment with a non-missing value, including those from unscheduled visits. If time is not collected, Day 1 assessments are assumed to be taken prior to first dose and used as baseline.

\*\*Baseline will be the average of the data collected from the 7-day period after Day -9 device dispense.

\*\*\*Exploratory Biomarkers and home exercise program will be analysed separately and will not be reported as part of this study Statistical Analysis Complete reporting.

Unless otherwise stated, if baseline data is missing no derivation will be performed and baseline will be set to missing.

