**7.2.3. Population of Interest**

The secondary efficacy analyses will be based on the Analysis Population. The decision-making endpoints PROactive endpoint, SGRQ, SPPB (time for repeated chair rise endpoint) and constant work rate (CWR) duration from endurance shuttle walking test will be also analysed based on the Per Protocol population.

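### Chair-rise time has no value for a participant who tries and cannot complete five stands after baseline, so a poor outcome on a decision-making endpoint is analysed as missing at random

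*SAP*

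**What the plan says.** The variable. SAP 12.6.2 (SPPB score and times) uses the CRF item "Time for five stands done successfully" as chair-rise time. Protocol 9.2.3.3 states: "The scores for each component and the time in seconds for each component will be recorded". Neither text gives a time, cap or rank for an attempt that falls short of five stands.

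Missing data. Protocol 10.2 states: "Missing values will not be imputed". SAP 12.7.2 only says that missing fields appear as blanks. By contrast, SAP 12.6.2 has explicit rules for incomplete SGRQ, CAT and PROactive data.

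The analyses. SAP 7.2.4.1 models change in chair-rise time at Days 28, 56 and 90 by MMRM, with a matching Bayesian model reporting posterior probabilities at 1.3 s and 1.7 s. SAP 7.2.3 lists the endpoint among those used for decision making. Table 2.28 (Bayesian, Analysis Population) is a headline result.

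The population. Inclusion criterion 4 (Protocol 6.1) requires "Timed chair stand score ≥1 AND ≤3" and bars a score of 0 on any SPPB component.

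**The concern.** A blank time here is not like a missed visit. The participant is still on treatment, came to the clinic and was tested. The time is absent because performance was too poor to produce one. A likelihood-based repeated-measures model, and its Bayesian counterpart, will implicitly predict that absent value from the person's earlier successful times and from the other participants in the arm. That is reasonable for data missing at random and wrong for data missing because of the outcome itself.

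Everyone enrolled starts with an impaired but completed chair stand, so loss of the ability is a plausible outcome, and one that an exercise-capacity objective should register. If more placebo participants lose it, benefit is understated on this endpoint. If more participants on active lose it, the endpoint looks better than it should. Either way the decision probabilities for chair-rise time are computed without the worst performers.

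**Working it through.** **1. Is there a stated figure to reproduce?** Not for this endpoint. The precision tables in Protocol 10.1.1 cover strength, lean mass, ISWT and ESWT only. As a check on the sample size they imply, the 90% half-width is t(0.95, 2n−2) × SD × √(2/n). For strength with SD 10.9 this gives 8.45 at n = 10 and 5.81 at n = 20, against 8.45 and 5.8 stated. So 20 evaluable per arm within each sex is the right n. No SD, expected effect or failure rate is given for chair-rise time, and everything below is illustrative.

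**2. How a failed attempt passes through the plan.**
- The time field is defined by success, so a failed attempt has no time (SAP 12.6.2).
- No value is supplied later (Protocol 10.2).
- The models use observed times only (SAP 7.2.4.1).
- Per Protocol exclusion 14 (SAP 12.1.1) refers to total SPPB score, not chair-rise time. A failed test with a recorded score can therefore remain in that population without a time.
- No table in SAP 12.11.5 counts failed attempts.

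**3. Effect of keeping failures.** Suppose k excess failures occur in one arm of 20, each assigned a time L seconds worse than the mean of those who completed. The arm mean, and so the difference, moves by k × L / 20.

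| k | L that moves the difference by 1.3 s (26/k) | L that moves it by 1.7 s (34/k) |
|---|---|---|
| 1 | 26 s | 34 s |
| 2 | 13 s | 17 s |
| 3 | 8.7 s | 11.3 s |
| 4 | 6.5 s | 8.5 s |

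With an assumed mean of 15 s and inability set at 30 s (L = 15), one failure moves the mean by 15/20 = 0.75 s and two by 1.5 s. With inability set at 25 s (L = 10), the shifts are 0.5 s and 1.0 s.

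**4. Effect of dropping failures.** Assume changes are normal and failures are the worst fraction q. The mean change among those who completed then shifts by −SD × φ(z)/(1−q), where z is the (1−q) normal quantile. The bias in active minus placebo is the active shift minus the placebo shift. Shorter is better, so a positive bias hides benefit.

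| Failure, placebo vs active | SD 2 s | SD 3 s | SD 5 s |
|---|---|---|---|
| 5% vs 5% | 0 | 0 | 0 |
| 10% vs 5% | +0.17 s | +0.26 s | +0.43 s |
| 20% vs 5% | +0.48 s | +0.72 s | +1.21 s |

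The sign reverses if active fails more often. The standard error of the difference is SD × √(2/20), or 0.95 s at SD 3. The last two rows are then 0.26/0.95 = 0.27 and 0.72/0.95 = 0.76 standard errors, enough to move a posterior probability near its middle range.

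These are completer-mean shifts. A repeated-measures model that borrows from earlier visits may recover part of the bias, so they indicate scale and do not predict a result.

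**The case against.** **Failure as missing is an inference.** No sentence says it. The CRF, the study reference manual and the SPPB scoring guide are not in the documents, and Protocol 9.2.3.3 does not limit recorded times to successes. This is fair, but the item's own label ties the time to success. If another convention exists, the SAP should state it.

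**Total SPPB score covers it.** It is analysed by MMRM in both populations and, if a failed stand scores 0, would register the loss. Chair-stand score and time are also listed by participant. This stands, and it limits the damage to one variable. A reader might infer that harm would be hidden from the trial; the documents do not support that. But the 1.3 s and 1.7 s probabilities use time alone.

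**Failures may be rare.** Exclusion 2 removes conditions that limit the physical assessments. Protocol 8.2 takes participants with severe or steroid-treated exacerbations off treatment, with safety-only follow-up, so they are dropouts and not attended failures. This is also fair, and no failure rate is given either way.

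**It is not the key endpoint.** Percent change in leg press strength is (SAP 5.5). True, which is why the proposal stops at a sensitivity analysis.

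**A stronger reading about baseline.** SAP 5.2 states: "Baseline value will be the latest pre-dose assessment with a non-missing value, including those from unscheduled visits". A reader might infer that someone who fails the chair stand on Day 1 routinely receives the better screening time as baseline. The protocol does not allow this to be routine. Day 1 assessments precede randomisation (Schedule of Activities), the SPPB criterion must be met before randomisation (Protocol 5.1), and Protocol 6.4 states: "Participants are expected to meet study entry criteria when they are randomized". A Day 1 failure is therefore a screen failure. The fallback matters only for a participant randomised in error, who would leave the Per Protocol population but stay in the Analysis Population. For a Day 1 time missing for other reasons, the rule is reasonable.

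**Conclusion.** The point holds for assessments after baseline. The plan has no rule for an attempted but uncompleted chair-rise test, and its definition, its bar on imputation and its models together treat that outcome as missing at random on a decision-making endpoint. Bias arises only if inability differs by arm. Its direction and size depend on failure rates that the documents do not give. Under the assumed SDs and failure rates it runs from 0 to about 1.2 s, against thresholds of 1.3 s and 1.7 s; a handful of unbalanced failures in an arm of 20 could matter, while rare or balanced failures would not. The conclusion rests on reading the CRF label literally and on a failed stand scoring 0. This is a worthwhile, inexpensive improvement to a secondary analysis and does not put the primary strength analysis in doubt.

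**What to change.** In SAP 12.6.2 and 7.2.4.1:

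1. Tabulate by sex, arm and visit the number with SPPB performed but five stands not completed, identified from the chair-stand component score.
2. Add a sensitivity MMRM and Bayesian analysis in the Analysis Population, in which such a post-baseline failure takes the longest time recorded in that sex cohort. Tests not performed for unrelated reasons stay missing. Report the probabilities at 1.3 s and 1.7 s beside those from the planned model.

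The main analysis is unchanged. The cost is SAP wording, one count table and the sensitivity outputs. Component scores and times are already recorded, and the SPPB listing shell (EFF_L4) already has columns for whether the SPPB was performed, the successful chair-stand time and the chair-stand score.

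There are two limits. The assigned time is arbitrary, so this stays a sensitivity analysis. It also needs the CRF to separate a failed attempt from one not made. The listing shell shows no chair-stand attempt or reason field, so this should be confirmed before the rule is fixed.
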